7.5.2 Patient-reported chronic GVHD symptoms (Chronic GVHD Activity Assessment Form B)

7.5.2.1 Skin itching

Subjects will complete an itching symptoms scale at visits indicated in Table 1. The scale requests the subjects to recall their worst itching symptoms in the past 7 days and score it on a scale of 0–10 with 0 = not present and 10 = as bad as you can imagine. The subject-reported skin-itching scale is part of the Chronic GVHD Activity Assessment eCRF. The Chronic GVHD Activity Assessment source document forms are in Appendix 7.

7.5.2.2 Skin and/or joint tightening

Subjects will complete a skin and/or joint tightening symptoms scale at visits indicated in Table 1. The scale requests the subjects to recall their worst skin and/or joint tightening symptoms in the past 7 days and score it on a scale of 0–10 with 0 = not present and 10 = as bad as you can imagine. The subject-reported skin-itching scale is part of the Chronic GVHD Activity Assessment eCRF. The Chronic GVHD Activity Assessment source document forms are in Appendix 7.

7.5.2.3 Mouth sensitivity

Subjects will complete a mouth sensitivity scale at visits indicated in Table 1. The scale requests the subjects to recall their worst mouth sensitivity symptoms in the past 7 days and score it on a scale of 0–10 with 0 = Not present and 10 = As bad as you can imagine. The subject-reported mouth-sensitivity scale is part of the Chronic GVHD Activity Assessment eCRF. The Chronic GVHD Activity Assessment source document forms are in Appendix 7.

7.5.2.4 *Genital discomfort*

Subjects will complete a genital discomfort scale at visits indicated in Table 1. The scale requests the subjects to recall their worst genital discomfort symptoms in the past 7 days and score it on a scale of 0–10 with 0 = not present and 10 = as bad as you can imagine. The subject-reported genital-discomfort scale is part of the Chronic GVHD Activity Assessment eCRF. The Chronic GVHD Activity Assessment source document forms are in Appendix 7.

7.5.2.5 *Eyes*

Subjects will complete an eyes symptom scale at visits indicated in Table 1. Subjects are asked to provide the main complaint with regard to their eyes and the associated severity on an 11-point scale ranging from 0–10 with 0 = not at all severe and 10 = most severe. The subject-reported eyes-symptoms scale is part of the Chronic GVHD Activity Assessment eCRF. The Chronic GVHD Activity Assessment source document forms are in Appendix 7.

7.5.3 Patient-reported global ratings (Chronic GVHD Activity Assessment Form B)

7.5.3.1 *Patient-Reported Overall Severity Scale*

The subject will complete the Patient-Reported Overall Severity Scale at visits indicated in Table 1. Subjects are asked to score how severe their chronic GVHD symptoms are on a scale of 0–10 with 0 = chronic GVHD symptoms not at all severe and 10 = most severe chronic GVHD symptoms possible. The Patient-Reported Overall Severity Scale is part of the Chronic GVHD Activity Assessment eCRF. The Chronic GVHD Activity Assessment source document forms are in Appendix 7.

7.5.3.2 *Patient-Reported Mild-Moderate-Severe Scale*

The subject will complete the Patient-Reported Mild-Moderate-Severe Scale at visits indicated in Table 1. Subjects are asked to report if they think their overall chronic GVHD is mild, moderate or severe. The Patient-Reported Mild-Moderate-Severe Scale is part of the Chronic GVHD Activity Assessment eCRF. The Chronic GVHD Activity Assessment source document forms are in Appendix 7.

7.5.3.3 *Patient-Reported 7-Point Change Scale*

The subject will complete the Patient-Reported 7-Point Change Scale at visits indicated in Table 1. Subjects are asked to compare their current chronic GVHD symptoms to one month prior on a scale of 7: +3 = very much better; +2 = moderately better; +1 = a little better; 0 = about the same; -1 = a little worse; -2 = moderately worse; -3 = very much worse. The Patient-Reported 7-Point Change Scale is part of the Chronic GVHD Activity

Confidential

Assessment eCRF. The Chronic GVHD Activity Assessment source document forms are in Appendix 7.

7.6 Exploratory biomarker assessments

7.6.1 Blood lymphocyte subsets

S1P₁ modulators such as ponesimod reduce total lymphocyte counts (T and B lymphocytes) in healthy subjects as a defined PD effect. T- and B-cells consist of different subsets having distinct functions in chronic GVHD disease manifestation and progression. Analysis of specific blood lymphocyte subsets provides a detailed understanding of the ponesimod effect on B and T lymphocyte subsets in a chronic GVHD patient population.

7.6.1.1 *Sampling time*

Blood samples for lymphocyte subsets will be taken from every subject at visits indicated in Table 1.

7.6.1.2 *Sampling procedure*

Up to 5 mL of blood is collected.

7.6.1.3 *Labeling and shipment*

Details of the collection, labeling and shipment of the samples can be found in the laboratory manual provided to the investigator. The tubes and labels for the samples will be provided to the investigator and/or staff by the sponsor or the central laboratory.

7.6.1.4 *Bioanalysis*

Blood samples will be analyzed by the sponsor following the principles of GCLP. The assays are validated for the purpose of exploration. B- and T-cell subsets are defined by a combination of cell surface markers and are analyzed in four separate panels (panel 1–4). The specified list of surface markers is not exhaustive.

- Panel 1: CD19, CD20, IgD, CD27, CD38, CD45, CXCR3, CD138
- Panel 2: CD3, CD4, CD8, CD45RA, CD25, CD45, CD127, CCR7
- Panel 3: CD3, CD4, CD8, CCR6, CXCR3, CXCR5, CD45, CRTH2
- Panel 4: CD45, CD19, CD10, CD21, CD 27, IgD

7.6.2 Plasma biomarkers

A recent report on biomarkers for chronic GVHD prepared by the NIH Biomarker Working Group identified several candidate biomarkers for the purpose of diagnosis, prognosis/risk stratification and prediction of treatment effect [NIH Biomarkers]. Biomarkers with

Confidential

sufficient evidence (cohesive findings in > 2 reports) will be investigated in plasma samples using assays validated for the purpose of exploration.

7.6.2.1 *Sampling time*

Plasma samples will be taken from every subject at visits indicated in Table 1.

7.6.2.2 *Sampling procedure*

5 mL of blood is collected in vacutainer tubes containing EDTA as anti-coagulant.

7.6.2.3 *Labeling and shipment*

Details of the collection, labeling and shipment of the samples can be found in the laboratory manual provided to the investigator. The tubes and labels for the samples will be provided to the investigator and/or staff by the central laboratory.

7.6.2.4 *Bioanalysis*

Plasma samples will be analyzed by the central laboratory. The assays will be validated for the purpose of exploration.

7.6.3 *Exploratory biomarker samples*

New scientific evidence on biomarkers related to chronic GVHD or S1P₁ modulators may trigger new analysis.

Research samples allow investigation of questions related to:

- A. Change of biomarker level over 24 weeks in a chronic GVHD patient population
- B. Baseline biomarker level in a chronic GVHD patient population
- C. Effect of ponesimod on biomarker level in a chronic GVHD patient population

Research samples are collected under the core ICF and can be stored by the sponsor for the duration specified in the core ICF.

7.6.3.1 *Sampling time*

Blood samples will be taken at visits indicated in Table 1.

7.6.3.2 *Sampling procedure*

5 mL of blood is collected in vacutainer tubes containing EDTA as anticoagulant.

7.6.3.3 *Labeling and shipment*

Details of the collection, labeling and shipment of the samples can be found in the laboratory manual provided to the investigator. The tubes and labels for the samples will be provided to the investigator and/or staff by the central laboratory.

Confidential

7.7 Total blood volume

The total blood volume to be drawn per subject during the Core Treatment Period is described in Table 7.

Table 7 Total blood volume drawn per subject - Core Treatment Period and Follow-up Period 1

Test	Number of tests	Volume per test	Total volume per scheduled study visits
Viral serology at screening	1	5 mL	5 mL
Interferon gamma release assay for tuberculosis at screening	1	3 × 1 mL	3 mL
Serum sample at baseline ¹	1	5 mL	5 mL
Hematology ²	12	3 mL	36 mL
Blood chemistry ³	12	7.5 mL	90 mL
Ponesimod pharmacokinetics ⁴	12	3 mL	36 mL
Blood lymphocyte subsets	3	5 mL	15 mL
Plasma biomarkers	3	5 mL	15 mL
Exploratory biomarker samples	3	5 mL	15 mL
Total blood volume drawn at scheduled study visits: 220 mL			

1. To be stored at the central laboratory for potential retrospective analyses of viral serology titers in the event of infections.
2. Additional samples may be needed in the event of absolute lymphocytes < 100 cells/µL and in case of a second serum pregnancy test prior to enrollment.
3. Includes serum pregnancy or post-menopausal test at screening, if needed.
4. Additional samples may be needed in the event of additional ECG measurements on Day 1 (Visit 2).

The total blood volume to be drawn per subject during the Extension Treatment Period is described in Table 8.

Table 8 Total blood volume drawn per subject - Extension Treatment Period and Follow-up Period 2

Test	Number of tests	Volume per test	Total volume per scheduled study visits
Hematology ¹	14	3 mL	42 mL
Blood chemistry	14	7.5 mL	105 mL
Total blood volume drawn at scheduled study visits: 147 mL			

1. Additional samples may be needed in the event of total lymphocytes < 100 cells/µL.

8 SCHEDULE OF VISITS AND ASSESSMENTS

A tabulated summary of all visits and assessments described in the following sections is provided in Table 1. The schedule of visit dates should be established at the time of

Confidential

screening. To the extent possible, subjects will be expected to adhere to the established visit schedule.

The time point for every visit is defined taking as a reference Day 1 (Visit 2), which is the day of enrollment.

When scheduling the different assessments for a subject visit, the following should be taken into account:

- The subject must come to the clinic before the morning administration of study drug, when applicable.
- At Visit 2 (Day 1), Visit 11 (EX-1) and on the days of re-initiation of study drug (if applicable), the assessments during the visits will be divided into two parts: before (pre-dose) and after (post-dose) the administration of ponesimod, which will be taken at the site on the day of visits.
- At other visits, ECGs, SBP/DBP, PFTs, blood drawings for hematology and blood chemistry, along with all other assessments, are to be performed pre-dose.
- Pre-dose PK samplings are to be done at Visits 2 (Day 1), 3 (Week 4), 4 (Week 8), 5 (Week 12), 6 (Week 16) and 7 (Week 20). Additional samples are drawn post-dose at Visits 2 (Day 1) and 5 (Week 12). At Visit 2, post-dose sampling must be drawn hourly at approximately the same time as post-dose ECGs are performed (as per Section 7.2.1.1). At Visit 5, the sample is collected 3 hours post-dose. A PK sample is also collected at EOT1, Visit 8 (Week 24); no study drug is taken at this visit.
- Resting time:
 - When the subject is to go to another department within the hospital for a specific test, sufficient time should be allowed for the subject to rest prior to the examination.
 - Sufficient time between blood drawing and cardiac assessments (i.e., ECGs and/or BP measurement) is to be allowed.
- Preferably, questionnaires will be completed by the subject in the morning prior to any other protocol assessment and prior to any other discussion with the investigator. Subjects will provide responses to the questionnaires while waiting for their appointment. Questionnaires should be completed prior to any discussion with the investigator in the following order:
 - Patient-reported chronic GVHD symptoms and patient-reported overall ratings (Chronic GVHD Activity Assessments Patient self-report Form B, [Appendix 7])
 - LSS

To ensure compliance, at each visit the study personnel must remind WOCBP to use the MOC defined for this study. The reminders must be documented in the eCRF.

Confidential

It is permitted to re-screen subjects once if the reason for non-eligibility was transient (e.g., abnormal laboratory test, insufficient wash-out period of a forbidden medication), provided that documented authorization has been received from Actelion. All pre-enrollment assessments should then be repeated at the time of re-screening (with the exception of CXR).

Unscheduled visits may be performed at any time during the study. Depending on the reason for the unscheduled visit (e.g., re-initiation of study drug, AE, central laboratory re-test, etc.), appropriate assessments may be required or may be performed based on the judgment of the investigator and must be recorded in the eCRF. After an unscheduled visit, the regular scheduled study visits must continue according to the planned visit and assessment schedule.

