	Visit window		± 7 days	± 7 days	± 7 days	+ 7 days
Extension Treatment inclusion/exclusion criteria*		X				
Chronic GVHD Activity Assessment, Form A and B*		X	X (Visit EX-4 only)	X	X	
Lee Symptom Scale*		X	X (Visit EX-4 only)	X	X	
Concomitant medications*		X	X	X	X	X
Physical examination*		X	X (Visit EX-4 only)	X	X	
Body weight*		X	X (Visit EX-4 only)	X	X	
Systolic/diastolic blood pressure*		X See Section 5.1.7	X (pre-dose)	X (pre-dose)	X	X
12-lead ECG (2)**		X See Section 5.1.7	X (pre-dose)	X (pre-dose)	X	X
Ophthalmological examination*			X (Visit EX-4 only)		X	
OCT (3)*			X (Visit EX-4 only)		X	
Spirometry*/DLCo*		X pre-dose	X (Visit EX-4 only) pre-dose	X pre-dose	X	X
Hematology**/Chemistry**/ Urinalysis		X pre-dose	X pre-dose	X pre-dose	X	X
Pregnancy test*/MOC* (5)		X urine	X urine	X urine (11)	X urine	X urine
PK and PD** sampling		X (PD only) pre-dose	X (PD only) (Visit EX-4 only) pre- dose	X (PD only) pre-dose	X (PD only)	X (PD only)
Study drug dispensing & accountability (6)**		X	X	X	X	
AEs & SAEs (7)*		X	X	X	X	X

*Data collected in the eCRF

**Electronically transferred to the sponsor

Confidential

Table 1 Visit and assessment schedule (continued)

Table notes

Day 1 (date of first study drug intake) is to be used as the reference date for the purpose of calculating the subsequent visit dates (and time windows).

- (1) Any chest X-ray that has been performed within 90 days prior to screening can be used (in this case, no need to repeat chest X-ray at screening).
- (2) In the event of a CTCAE grade 2 QTc elevation identified on 12-lead ECG (QTc 481–500 ms), a 12-lead ECG must be repeated 3 hours post dose. The subject is prematurely discontinued if the repeated QTcF > 500 ms.
- (3) OCT is performed at indicated visits plus any visit in case of visual symptoms suggestive of macular edema.
- (4) Investigator must review all test results prior to permitting subject to start the 4-day up-titration at Visit 3 and/or the dose escalation to 20 mg at Visit 4.
- (5) For women of child-bearing potential, the serum pregnancy test at Visit 1 must be performed at least 3 weeks before a urine pregnancy test at Visit 2. A second serum pregnancy may be performed instead of the urine test as early as 7 days after the first serum pregnancy test, and enrollment can begin as soon as the negative result is available. Assess and reinforce continued use of MOC for women of child-bearing potential at every visit.

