18. Active or latent tuberculosis (TB), as assessed by chest X-ray (CXR) performed at screening or within 90 days prior to screening, and interferon gamma release assay (QuantiFERON-TB-Gold[®]) at screening, except if there is documentation that the subject has received adequate treatment for TB previously.
19. Congenital or acquired severe immunodeficiency or known human immunodeficiency virus (HIV) or positive HIV testing at screening.

Malignancy

20. New or recurrent malignancy or minimal residual disease.

Metabolic

21. Type 1 or 2 diabetes that is poorly controlled according to investigator judgment or diabetes complicated with organ involvement such as nephropathy or retinopathy.

Ophthalmologic

22. Presence of macular edema.

Pregnancy and breastfeeding

23. Breastfeeding, pregnant women or women planning to become pregnant during the study.

Pulmonary

24. Subjects with a clinically significant pulmonary condition including asthma and chronic obstructive pulmonary disease (COPD) that is insufficiently controlled according to investigator judgment.

25. Subjects with diagnosed BOS.

26. Subjects with any hospitalization due to a clinically significant pulmonary condition including asthma or COPD exacerbation within 24 weeks prior to screening (with the exception of a fully resolved pulmonary infection).

27. Subjects with abnormal PFTs: $FEV_1 < 60\%$ of predicted normal value or $FEV_1/forced vital capacity (FVC) < 0.7$ at screening.

Renal

28. Severe renal insufficiency defined as a calculated creatinine clearance $< 30 \text{ mL/min}/1.73 \text{ m}^2$ (Cockcroft-Gault) at screening.

Treatments

29. Systemic glucocorticoids at prednisone-equivalent dose $> 1.0 \text{ mg/kg/day}$ at screening.

30. Treatment within 15 days prior to enrollment with:

- Azathioprine
- β -blockers, diltiazem, verapamil, digoxin, digitoxin or any anti-arrhythmic or HR-lowering systemic therapy (a non-exhaustive list of drugs provided in Appendix 4)
- CsA, TAC, MMF, MPS, EVL, SRL (with the exception of any therapy serving as a mandatory concomitant therapy, as per inclusion criterion 4 and Section 5.2).
- Extracorporeal photopheresis
- Isotretinoin

- Thalidomide

31. Treatment within 30 days prior to enrollment with:

- Acitretin
- Cyclophosphamide
- Etanercept
- Imatinib
- Vaccination with live vaccines

32. Treatment within 45 days prior to enrollment with:

- Pulse methylprednisolone

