7.3.5 Chest X-ray

A CXR will be performed at Visit 1 (screening), and assessed by the local radiologist in order to exclude any subject with findings suggestive of active or latent TB. Any CXR that had been performed within 90 days prior to screening can be used; if available, there is no need to repeat CXR at screening.

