7.3.6 Test for tuberculosis

An interferon gamma release assay (QuantiFERON-TB-Gold[®]) will be performed at Visit 1 (screening) to screen for active or latent TB. The test will be analyzed and interpreted at the central laboratory [see Section 7.3.11] and electronically transferred to the sponsor.

Only subjects with a negative test at screening and without CXR findings [see Section 7.3.5] at screening or within the previous 90 days suggestive of active or latent TB can be included in the study. If the test result is positive, subjects must not be included in the study, except if there is documentation that the subject has received adequate treatment for TB previously. If the test result is inconclusive (invalid, indeterminate, or borderline), the test may be repeated once and a negative result must be obtained prior to enrollment in order to include the subject. If the result of the repeated test is again inconclusive (invalid, indeterminate, or borderline), subjects must not be included in the study.

Details on the performance of the test for TB will be provided in the specific central laboratory manual.

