8.1 Screening period

The screening period must take place within 30 days prior to enrollment and include the Visit 1 (screening) and the pre-dose assessments of Visit 2 (Day 1).

The start of screening occurs on the day the first screening assessment was performed (i.e., signature of informed consent).

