8.1.1 Visit 1 (screening)

Visit 1 will be performed from 30 days to 1 day prior to enrollment. The Visit 1 date is defined as the date of the first assessment performed for the study (i.e., informed consent signature). During this visit, subject informed consent will be obtained, and assessments required for the determination of subject eligibility will be performed. These assessments may generally be performed on separate days within the screening period.

Visit 1 includes:

- After discussing the study with the investigator and after agreeing to study participation by signing the ICF, subjects will be assigned a subject number by the interactive response technology (IRT) provider. For any subject, it is the responsibility of the investigator to obtain written informed consent (subject's signature) prior to performing any protocol-mandated assessment. However, assessments performed as part of the routine care of the subject may be used to assess eligibility. The subject number will identify the subject throughout the study. In case of re-screening [see Section 8], the subject number assigned during the first screening procedure will be retained.
- Review of chronic GVHD diagnosis and assess stage and score per 2014 NIH consensus criteria [Appendix 2]
- Recording of demographics, medical history, smoking status, and disease characteristics

Confidential

- Recording of previous and concomitant medications [see Section 5.2]
- SBP/DBP
- Body weight and height
- Physical examination
- Spirometry (under the responsibility of the pulmonologist)
- DLCo (under the responsibility of the pulmonologist)
- Ophthalmological examination (under the responsibility of the ophthalmologist)
- OCT (under the responsibility of the ophthalmologist)
- Hematology, blood chemistry, serum pregnancy test for WOCBP and exploratory biomarker assessments (blood lymphocyte subsets, plasma biomarkers, exploratory biomarker samples)
- TB test
- Viral serology
- Urinalysis
- 12-lead ECG
- CXR (any CXR performed within 90 days prior to screening can be used). In case of rescreening, CXR does not need to be repeated.
- Recording of AEs/SAEs: all AEs/SAEs occurring after signing of the ICF are to be reported in the eCRF and on an SAE form, if applicable.

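### The re-screening exemption from a repeat chest X-ray has no limit on film age, which is inconsistent with the 90-day window in exclusion 18 once the film is more than 90 days old at re-screening

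*Combined protocol and SAP*

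**What the plan says.** Five places tie the chest X-ray to a 90-day window. Exclusion 18, in Section 4.4 and the synopsis, reads "Active or latent tuberculosis (TB), as assessed by chest X-ray (CXR) performed at screening or within 90 days prior to screening" and adds an interferon gamma release assay at screening. Section 7.3.5 says "Any CXR that had been performed within 90 days prior to screening can be used". Section 7.3.6 admits only subjects with a negative assay and no film findings "at screening or within the previous 90 days suggestive of active or latent TB can be included in the study", with an exception for documented adequate earlier treatment. Table 1 note 1 says "Any chest X-ray that has been performed within 90 days prior to screening can be used". Section 4.4 allows no waiver of any exclusion criterion.

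Two places exempt re-screened subjects. Section 8 permits one re-screening for a transient reason, with documented sponsor authorization, and continues: "All pre-enrollment assessments should then be repeated at the time of re-screening (with the exception of CXR"). Section 8.1.1 restates the 90-day window for the film and then adds "In case of rescreening, CXR does not need to be repeated".

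On timing, Section 8.1 says "The screening period must take place within 30 days prior to enrollment". Section 8.1.1 places Visit 1 between 30 days and 1 day before enrollment. No section sets a maximum interval between the first screening and the re-screening.

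**The concern.** The exemption is unconditional, while the window it bears on is a fixed number of days. Section 8 names an incomplete wash-out of a forbidden medication as one transient reason to re-screen, and some listed wash-outs last many months. The film from the first screening, which may already have been up to 90 days old then, can therefore stand in for a re-screening that takes place much later.

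The film is one of the two named tuberculosis checks made before a lymphocyte-lowering drug is added to mandatory background immunosuppression. If sites resolve the two rules differently, some re-screened subjects will enter on a film outside the protocol's own window and others will not. The first group may later be classed as eligibility deviations. Sample size, power and the primary analysis are not affected.

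**Working it through.** The documents state no figure for film age on the re-screening path, so there is none to reproduce. The check is a comparison of the text followed by day counts.

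**Which screening does exclusion 18 refer to?** Section 8.1 requires the screening period to fall within the 30 days before enrollment. For a subject enrolled more than 30 days after the first screening, only the re-screening lies in that period. The most natural reading is therefore that the 90 days run back from the re-screening visit.

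**When do the rules conflict?** Let *a* be the film's age at first screening (0 to 90 days) and *g* the days from first screening to re-screening. The film's age at re-screening is *a* + *g*. Both rules are satisfied when *a* + *g* ≤ 90. When *a* + *g* > 90, exclusion 18 calls for a newer film and Sections 8 and 8.1.1 do not.

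**Ordinary path.** Film at most 90 days old at screening, screening at most 30 days before enrollment: 90 + 30 = 120 days at enrollment.

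**Re-screening path, illustrative.** The documents give no maximum gap, so I take the wash-out lengths in Section 4.4 as an assumption. First screening falls on the day of the last excluded dose, and enrollment on the first day the wash-out *w* is complete. Then:

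- film age at enrollment = *a* + *w*, with *a* from 0 to 90;
- smallest film age at re-screening = *w* − 30 (film taken on the first screening day, re-screening as early as allowed).

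| Wash-out | *w* (days) | Film age at enrollment (days) | Smallest film age at re-screening (days) |
|---|---|---|---|
| 60 days (e.g. basiliximab) | 60 | 60 to 150 | 30 |
| 24 weeks (e.g. rituximab) | 168 | 168 to 258 | 138 |
| 36 weeks (hydroxychloroquine) | 252 | 252 to 342 | 222 |
| 48 weeks (e.g. alemtuzumab) | 336 | 336 to 426 | 306 |

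In the 24-, 36- and 48-week rows the film is past 90 days at re-screening even if it was taken on the first screening day. In the 60-day row a fresh film stays inside the window: at most 59 days old if re-screening is 1 day before enrollment. A film already 90 days old at first screening does not: it is 120 to 149 days old at re-screening.

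**With the exemption limited to films no more than 90 days old at re-screening,** the maximum at enrollment returns to 90 + 30 = 120 days.

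**The case against.** The strongest reply is that the exemption is a deliberate exception. It appears twice, once directly beside the 90-day rule, and exclusion 18 speaks of screening without mentioning re-screening. If that word meant the first screening, the original film would satisfy the criterion. This reading cannot be ruled out, so part of the problem is ambiguity. It fits poorly with the 30-day rule in Section 8.1, however, and it would leave film age at enrollment with no limit at all. The opposite reply, that the 90-day limit still applies silently, makes the exemption nearly redundant: a film within 90 days of re-screening is already usable under Section 8.1.1.

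A reader might infer that a site following Section 8 necessarily enrolls a subject whom exclusion 18 bars. The documents do not support that. The wording says a repeat is not needed and does not forbid one. Eligibility is governed by Section 4.4 without waivers and is checked again at Visit 2, so a site applying exclusion 18 strictly would obtain a new film.

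A reader might also set 258 or 426 days against the 90-day limit. That mixes two reference points: wash-outs run to enrollment, while the 90 days run to screening. The like-for-like comparator at enrollment is 120 days.

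The safeguards also stand. The assay is repeated at re-screening, active infection is excluded separately, and re-screening is allowed once with documented sponsor authorization. No section asks the sponsor to consider the film's age when authorizing it.

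**Conclusion.** The inconsistency is real but minor. Sections 8 and 8.1.1, followed as written, permit a film outside the window that exclusion 18, Sections 7.3.5 and 7.3.6 and Table 1 note 1 all use. This arises only when the film is more than 90 days old at re-screening.

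The long ages in the table are stacked worst cases. They assume a first screening on the day of the last excluded dose and, at the upper end, a film already 90 days old. They also assume that the sponsor authorizes a wait of that length as transient. Nothing in the documents suggests that such cases are expected to be common in a study of 30 subjects, and a laboratory abnormality, Section 8's other example, could mean a shorter gap. The conclusion rests on reading screening in exclusion 18 as the re-screening for a subject who returns late, which Section 8.1 favors but does not state outright.

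**What to change.** Reconcile Sections 8 and 8.1.1 with exclusion 18. State in both places that the chest X-ray need not be repeated at re-screening provided it was performed within 90 days before the re-screening visit. This applies the protocol's existing window and introduces no new limit. If the sponsor did intend exclusion 18 to run from the first screening, the criterion should say so, together with the oldest film that is acceptable at enrollment.

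The change is one clause in two places. Its cost is a repeat of an already planned film for the few subjects re-screened with an older one.
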